10.1 Imaging Studies

CT, and optional PET scans are to be performed during Screening and within 7 days prior to starting Cycle 3. The CT, and optional PET scans will be done at Investigator's discretion thereafter, but not longer than every 6 months. Either CT or PET/CT scan may utilized, at the discretion of the investigator.

Other appropriate imaging studies (e.g., MRI, CT, X-ray) to document sites of disease are to be performed during Screening per standard of care, as determined by the Investigator. Appropriate imaging studies are to be repeated as necessary to confirm CR.

10.2 Bone Marrow Examination

Optional bone marrow aspiration and trephine biopsy are to be performed for patients during Screening. Bone marrow aspiration and biopsy are to be repeated during treatment as clinically indicated, at the Investigator's discretion, and in order to confirm CR.

10.3 Assessment of Disease Response

After discontinuation of therapy, patients are to have disease response assessed at the discretion of the treating physician, but not longer than every 6 months. Bone Marrow biopsy will be required after cycle 2 for patients with bone marrow involvement at baseline who have a complete response by imaging and physical exam

10.3.1 Definitions

Evaluable for objective response. Patients who have received at least one day of therapy, and have had their disease re-evaluated will be considered evaluable for response. These patients will have their response classified according to the definitions stated below. Patients who exhibit objective disease progression prior to the end of cycle 1 will also be considered.

Measurable disease. Measurable lesions are defined as those that can be accurately measured in two dimension (longest diameter to be recorded) as ≥ 20 mm with conventional techniques (PET/CT, MRI, x-ray) or as ≥ 10 mm with spiral CT scan. All tumor measurements will be recorded in millimeters (or decimal fractions of centimeters). Tumor volume will be recorded as the sum of the product of the diameters (SPD) of the largest predominant target lesions.

FDG avidity is based on comparison with background tissues. There is no specific SUV value that is considered a cut-off.

Non-measurable disease (evaluable disease). All other lesions (or sites of disease), including

small lesions (<10 mm using spiral CT scan), are considered non-measurable disease. Bone lesions, leptomeningeal disease, ascites, pleural/pericardial effusions, lymphangitis cutis/pulmonitis, inflammatory breast disease, abdominal masses (not followed by CT or MRI), and cystic lesions are all non-measurable.

Target lesions. All measurable lesions up to a maximum of 6 lesions total, representative of all involved organs, should be identified as target lesions and recorded and measured at baseline. Target lesions should be selected on the basis of their SUV avidity (High SUV lesions will be prioritized, even if not the largest lesions) and size (lesions with the largest SPD diameter) and their suitability for accurate repeated measurements (either by imaging techniques or clinically). An SPD for all target lesions will be calculated and reported as the baseline sum SPD. The baseline sum SPD will be used as reference by which to characterize the objective tumor response based on CT criteria.

Non-target lesions. All other lesions (or sites of disease) including any measurable lesions over and above the 6 target lesions should be identified as non-target lesions and should also be recorded at baseline. Measurements of these lesions are not required, but the presence or absence of each should be noted throughout follow-up.

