10.4 Response Criteria

10.4.1 Evaluation of Measurable Disease in Lymphoma

Table 5 outlines the response criteria used to evaluate disease response to therapy.

Table 5 : Response Criteria for NHL

Response	Definition	Nodal Masses	Spleen/Liver	Bone Marrow CR
CR	Disappearance of all evidence of disease	a) FDG-avid or PET positive prior to therapy; mass of any size permitted if PET negative (b) Variably FDG-avid or PET negative; regression to normal size on CT	Not palpable, nodules disappeared	Infiltrate cleared on repeat biopsy; if indeterminate by morphology, immunohistochemistry should be negative
PR	Regression of measurable disease and no new sites	50% decrease in SPD of up to 6 largest dominant masses; no increase in size of other nodes (a) FDG-avid or PET positive prior to therapy; one or more PET positive at previously involved site (b) Variably FDG-avid or PET negative; regression on CT	50% decrease in SPD of nodules (for single nodule in greatest transverse diameter); no increase in size of liver or spleen	Irrelevant if positive prior to therapy; cell type should be specified
SD	Failure to attain CR/PR or PD	(a) FDG-avid or PET positive prior to therapy; PET positive at prior sites of disease and no new sites on CT or PET (b) Variably FDG-avid or PET negative; no change in size of previous lesions on CT		
Relapsed or PD	Any new lesion or increase by 50% of previously involved sites from nadir	Appearance of a new lesion(s) 1.5 cm in any axis, 50% increase in SPD of more than one node, or 50% increase in longest diameter of a previously identified node 1 cm in short axis Lesions PET positive if FDG-avid lymphoma or PET positive prior to therapy	50% increase from nadir in the SPD of any previous lesions	New or recurrent involvement

Abbreviations: CR, complete remission; FDG, [18F]fluorodeoxyglucose; PET, positron emission tomography; CT, computed tomography; PR, partial remission; SPD, sum of the product of the diameters; SD, stable disease; PD, progressive disease.

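### With more than six measurable lesions, Section 10.3.1 and Table 5 can grade partial response on different lesions, and Table 5's bar on growth in other nodes need not be documented

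*Combined protocol and SAP*

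**What the plan says.** Section 10.3.1 limits the target set: "All measurable lesions up to a maximum of 6 lesions total, representative of all involved organs". Within that limit it ranks lesions by uptake: "Target lesions should be selected on the basis of their SUV avidity (High SUV lesions will be prioritized, even if not the largest lesions". The sentence goes on to list "and size (lesions with the largest SPD diameter) and their suitability for accurate repeated measurements". The chosen set then drives response: "The baseline sum SPD will be used as reference by which to characterize the objective tumor response based on CT criteria".

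Any measurable lesion beyond the six becomes non-target, and for these "Measurements of these lesions are not required, but the presence or absence of each should be noted throughout follow-up".

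Table 5 in Section 10.4.1 defines nodal PR differently: "50% decrease in SPD of up to 6 largest dominant masses; no increase in size of other nodes".

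Two further provisions matter. Uptake is known only where PET was done, and Section 10.1 makes PET optional: "CT, and optional PET scans are to be performed during Screening and within 7 days prior to starting Cycle 3". The definition of measurable disease calls for lesions "accurately measured in two dimension (longest diameter to be recorded", while SPD needs two diameters per lesion. Section 10.4.2 separately counts unequivocal progression of a non-target lesion as PD. Section 10.4.4 builds ORR, the primary endpoint, from each patient's best response.

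**The concern.** PR is half of the primary endpoint, CR + PR, and it feeds the two-stage decision. The protocol gives two rules for which lesions are summed and does not say which prevails. A large mass with low uptake belongs in the Table 5 sum but can be left out under Section 10.3.1. Once it is left out, the case record need only say that it is still there, so nothing has to document whether it grew. Table 5 would withhold PR for such growth.

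The target set also depends on whether the investigator chose PET. Two patients with the same CT findings could therefore be assessed on different lesions.

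**Working it through.** The plan gives no figure to reproduce. The check compares the two rules and then applies both to assumed lesion sizes.

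**1. When the sets can differ.** With six or fewer measurable lesions, all of them are targets and there is no selection conflict. With seven or more, Section 10.3.1 puts uptake first and Table 5 uses size.

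**2. What is recorded from the seventh lesion on.** Section 10.3.1 requires presence or absence. Table 5 needs to know that other nodes have not enlarged, and presence or absence does not show that.

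**3. Illustration (assumed sizes).** Six high-uptake nodes of 2.0 x 2.0 cm shrink to 1.3 x 1.3 cm. One low-uptake mass in the same organ system measures 8 x 6 cm at baseline, and each of its diameters is multiplied by s. Nodes of 20 mm meet both measurability thresholds in Section 10.3.1 (20 mm by conventional technique, 10 mm by spiral CT).

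- Uptake-first targets (six nodes): 6 x 2.0 x 2.0 = 24.0 cm2, falling to 6 x 1.3 x 1.3 = 10.14 cm2. Change: 10.14/24.0 - 1 = -58%. The 50% cut is met.
- Six largest (mass plus five nodes): baseline 48 + 5 x 4 = 68 cm2; follow-up 48s² + 5 x 1.69 = 48s² + 8.45 cm2.

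| s | Follow-up SPD of six largest (cm2) | Change from 68 |
|---|---|---|
| 1.00 | 56.45 | -17% |
| 1.05 | 61.37 | -10% |
| 1.10 | 66.53 | -2% |
| 1.20 | 77.57 | +14% |

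None of these is PR under Table 5. None is PD either: only one lesion enlarges, and its longest diameter grows by at most 20% against the 50% required. At s = 1.20 its area is up 44%. The patient is SD under Table 5 and meets the PR cut on the Section 10.3.1 targets, even when the mass has not grown at all.

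Smaller nodes behave the same way, but need spiral CT to be measurable. Six nodes of 15 x 12 mm shrinking to 10 x 8 mm take target SPD from 1080 to 480 mm2 (-56%). A mass growing from 80 x 60 to 95 x 70 mm takes the six-largest SPD from 4800 + 5 x 180 = 5700 to 6650 + 5 x 80 = 7050 mm2 (+24%). Its longest diameter rises 95/80 - 1 = 19%.

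**4. The opposite error.** Let the 8 x 6 cm mass shrink to 4 x 3 cm while the six 2.0 cm nodes stay unchanged. Uptake-first SPD is 24.0 before and after (0%), so SD. The six-largest SPD goes from 68 to 12 + 20 = 32 cm2 (-53%), so PR under Table 5. Uptake-first selection can therefore miss a response as well as create one.

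**5. Size on the endpoint.** One patient is 1/40 = 2.5 points of ORR at full size, or 1/22 = 4.5 points at stage 1. Under Section 12.1.2, two responses among 22 open stage 2 and the mantle cell cohort, so one misclassified patient can be half of that count.

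**6. Sensitivity (assumed rates).** Take one reading of the design: continue at 2 or more of 22, and declare success at 8 or more of 40 in total. P(success) is the sum over x = 2 to 22 of P(X1 = x) times P(X2 ≥ 8 - x), with X1 ~ Bin(22, p) and X2 ~ Bin(18, p). At p = 0.15 this is 24.3%. A net 1, 2 or 3 points of false PRs raises it to 30.3%, 36.6% or 43.2%. The documents give no basis for any of these rates. The gap between 24.3% and the stated 0.05 is a separate matter.

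**The case against.** The strongest reply is that the protocol already guards against a growing mass. Section 10.4.2 makes unequivocal non-target progression PD, lets the treating physician's opinion prevail, and asks for later confirmation by a review panel or the Principal Investigator. That stands for obvious growth. It sets no size threshold, though, while Table 5 withholds PR for any enlargement of other nodes. It does nothing about a stable mass that simply drops out of the sum.

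Section 10.4.2 also labels persistence of a non-target lesion as incomplete response or SD. It gives no rule for combining that label with the target result. Read as an overall grade, it would deny PR to anyone with a persisting non-target lesion, which Table 5 does not do.

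Other points narrow the issue without removing it:

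- Size and measurability are listed criteria, and targets should represent all involved organs, so many bulky masses would be chosen anyway. Uptake is still expressly ranked above size.
- Measuring other lesions is not required, but it is not barred, and the scans exist. A careful reader could apply Table 5 in full. The plan does not oblige anyone to record it.
- The measurable-disease wording already refers to two dimensions and Section 10.3.1 requires an SPD, so the phrase about the longest diameter needs clarifying and is not a separate fault.
- Table 5 itself grades by PET status, so dependence on PET does not come from Section 10.3.1 alone.

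**Conclusion.** The two sections conflict as written and should be reconciled, because the conflict bears on the primary endpoint and the stage 1 count. It is confined to patients with more than six measurable lesions. Within that group, a large mass that is stable, or growing but not unequivocally, can be left out of the target SPD; the patient can then be PR under Section 10.3.1 and SD under Table 5. Each such patient moves ORR by 2.5 points in 40 or 4.5 points in 22. The frequency is unknown, and the lesion sizes above are assumed.

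A reader might infer two stronger conclusions that the documents do not support. One is that growth of a bulky non-target mass goes wholly unnoticed and never leads to PD; Section 10.4.2 covers the unequivocal case, and in the examples Table 5 would not call PD either. The other is that ORR is biased upward overall. Lesion selection can err in both directions, as step 4 shows. Only the missing non-target measurements push one way, since an unrecorded increase can fail to block a PR but cannot remove one.

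**What to change.** State in Section 10.3.1 that Table 5 governs, and align the definitions with it:

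- Define target lesions as the six largest dominant measurable masses on CT, or all of them if there are fewer.
- State that both perpendicular diameters of each target lesion are recorded, since SPD needs them.
- Replace the sentence that waives measurement of non-target lesions with a requirement to record the longest diameter of the remaining measurable nodes at baseline and at each scheduled response scan.
- Reconcile the non-target wording in Section 10.4.2 with Table 5, including how target and non-target findings combine into one response.

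The cost is protocol and case report form wording, plus a few extra measurements on scans already taken. No additional imaging is needed.

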10.3.2 Methods for Evaluation of Measurable Disease in Lymphoma

All measurements should be taken and recorded in metric notation using a ruler or calipers. All baseline evaluations should be performed as closely as possible to the beginning of treatment and never more than 4 weeks before the beginning of the treatment.

The same method of assessment and the same technique should be used to characterize each identified and reported lesion at baseline and during follow-up. Imaging-based evaluation is preferred to evaluation by clinical examination when both methods have been used to assess the antitumor effect of a treatment.

Clinical lesions: Clinical lesions will only be considered measurable when they are superficial (e.g., skin nodules and palpable lymph nodes). In the case of skin lesions, documentation by color photography, including a ruler to estimate the size of the lesion, is recommended.

CT, PET/CT and MRI: These techniques should be performed with cuts of 10 mm or less in slice thickness contiguously. Spiral CT should be performed using a 5 mm contiguous reconstruction algorithm. This applies to tumors of the chest, abdomen, and pelvis. Head and neck tumors and those of extremities usually require specific protocols.

Ultrasound (US): Will not be used for disease assessment

10.4 Response Criteria

10.4.1 Evaluation of Measurable Disease in Lymphoma

Table 5 outlines the response criteria used to evaluate disease response to therapy.

Table 5 : Response Criteria for NHL

Response	Definition	Nodal Masses	Spleen/Liver	Bone Marrow CR
CR	Disappearance of all evidence of disease	a) FDG-avid or PET positive prior to therapy; mass of any size permitted if PET negative (b) Variably FDG-avid or PET negative; regression to normal size on CT	Not palpable, nodules disappeared	Infiltrate cleared on repeat biopsy; if indeterminate by morphology, immunohistochemistry should be negative
PR	Regression of measurable disease and no new sites	50% decrease in SPD of up to 6 largest dominant masses; no increase in size of other nodes (a) FDG-avid or PET positive prior to therapy; one or more PET positive at previously involved site (b) Variably FDG-avid or PET negative; regression on CT	50% decrease in SPD of nodules (for single nodule in greatest transverse diameter); no increase in size of liver or spleen	Irrelevant if positive prior to therapy; cell type should be specified
SD	Failure to attain CR/PR or PD	(a) FDG-avid or PET positive prior to therapy; PET positive at prior sites of disease and no new sites on CT or PET (b) Variably FDG-avid or PET negative; no change in size of previous lesions on CT		
Relapsed or PD	Any new lesion or increase by 50% of previously involved sites from nadir	Appearance of a new lesion(s) 1.5 cm in any axis, 50% increase in SPD of more than one node, or 50% increase in longest diameter of a previously identified node 1 cm in short axis Lesions PET positive if FDG-avid lymphoma or PET positive prior to therapy	50% increase from nadir in the SPD of any previous lesions	New or recurrent involvement

Abbreviations: CR, complete remission; FDG, [18F]fluorodeoxyglucose; PET, positron emission tomography; CT, computed tomography; PR, partial remission; SPD, sum of the product of the diameters; SD, stable disease; PD, progressive disease.

10.4.2 Response Definitions

Complete Response (CR): Disappearance of all non-target lesions by PET/CT

Incomplete Response/Stable Disease (SD): Persistence of one or more non-target lesion(s) and/or maintenance of tumor marker level above the normal limits

Progressive Disease (PD): Appearance of one or more new lesions and/or unequivocal progression of existing non-target lesions

Although a clear progression of “non-target” lesions only is exceptional, the opinion of the treating physician should prevail in such circumstances, and the progression status should be confirmed at a later time by the review panel (or Principal Investigator).

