- The anti-tumor activity of ACY-1215, as measured by:
 - Objective response rate (complete response [CR] + partial response [PR]) assessed according to International Harmonization Project revised Criteria (2007)

Secondary endpoints of the study are to:

- Define the duration of response
- Define the rate of progression free survival
- Define safety and adverse events
- Define the exposure response analyses including biomarkers relating to intracellular protein acetylation.
- Describe the Single- and multiple-dose ACY-1215 pharmacokinetic profile.
- Describe changes in MRS signals with response to study drug

Sample Size

Phase Ib:

Three patients will be sequentially enrolled in one of two cohorts: Arm A and Arm B for a total of six patients (3 in each arm). If $\leq 33\%$ of patients ($N \leq 1$) experiences a dose limiting toxicity (DLT) in a cohort, the cohort will be expanded to 6 patients (3+3). If there are $\leq 33\%$ ($N \leq 2$ DLTs), the cohort will be further expanded to a total of 10 patients (3+3+4). The maximum total number of patients for both Arms A and B with full expansions will total of 20. If more than 1/3 or 2/6 patients experience a DLT, there will be no expansion.

Phase II:

Utilizing the Simon 2 Stage Minimax design, an estimated 40 patients will be needed to determine efficacy at a power of 0.80 and type I error of 0.05. For Stage I, 22 patients

will be enrolled of which 2 must achieve a response to allow for recruitment of patients into Stage 2. Stage 2 will enroll 18 patients of which 8 responses would be needed to attain an efficacy of 25%. An expansion cohort of 20 patients with relapsed or refractory mantle cell lymphoma patients will be assessed to evaluate efficacy in this subtype. The total number of patients accrued to the Phase II component of the study will equal 60.

Safety

Patients will be monitored carefully for the development of adverse events as well as clinical and/or radiographic evidence of disease response. Adverse events will be evaluated according to criteria outlined in the NCI Common Terminology Criteria for Adverse Events (CTCAE), version 4.0.

Figure 1: Schema

[figure not shown]

TABLE OF CONTENTS

	Page
1. OBJECTIVES	1
1.1 Phase Ib	1
1.2 Phase II	1
2. BACKGROUND	1
2.1 Background on lymphoid Malignancies	1
2.2 ACY-1215	2
2.3 Rationale for Phase Ib Study Design	11
3. PATIENT SELECTION	12
3.1 Inclusion Criteria for Lymphoma	12
3.2 Exclusion Criteria	13
3.3 Inclusion of Women and Minorities	13

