Patients will be evaluated for disease response with CT or PET/CT after cycles 2 and 6, then at the investigators discretion with intervals no more than 6 months. Patients who withdraw from the study will be required to have an End of Study Visit 4 weeks (+/- 7 days) after the last study drug dose. After discontinuation of therapy, patients will be followed on an approximately every 3 month basis (+/- 1 week) until development of PD or initiation of alternative therapy in order to determine the duration of response.

Safety will be evaluated during the study by documentation of AEs and SAEs, clinical laboratory tests (hematology, clinical chemistry, and urinalysis), physical examinations, vital sign measurements, and 12-lead ECGs.

The anti-tumor activity of ACY-1215 will be determined by CT or PET/CT and assessment of disease response will be evaluated using the International Harmonization Project revised Criteria (2007) [27].

Exposure-response of ACY-1215 including biomarkers relating to intracellular protein acetylation, IL6 and IL10 secretion, and markers of the UPR will be analyzed as a function of treatment and response.

Serial blood samples will be collected for determination of the single- and multiple-dose PK of ACY-1215. Patients will receive ACY-1215 160mg orally (PO) for 28 consecutive days per cycle according to schedule determined by the Phase Ib. There will be no limit to the number of cycles patients will receive.

Table 1: Regimen Description

REGIMENT DESCRIPTION						
Agent	Premedications; Precautions	Dose	Route	Frequency	Schedule	Cycle Length
ACY-1215	None	160mg (1 vial)	PO	Once daily vs. Twice daily	Days 1-28	28 days

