The following section describes the anti-tumor measurements that will be obtained during the study. Response will be evaluated with physical exam, computerized tomography (CT) and optional Positron emission tomography (PET) scans, and tissue biopsies as defined by the guidelines of the International Harmonization Project Group 2007 Revised Response Criteria [27].

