12.1 Statistical Methods

12.1.1 Phase Ib:

The study will follow the similar principles of a standard 3+3 dose escalation study in which less than one third of patients enrolled to a particular Arm must not have a dose limiting toxicity to allow for expansion. Three patients will be sequentially enrolled in one of two cohorts: Arm A and then after a safety assessment has occurred, Arm B for a total of six patients (3 in each arm). If $\leq 33\%$ of patients ($N \leq 1$) experiences a dose limiting toxicity (DLT) in a cohort, the cohort will be expanded to 6 patients. If there are $\leq 33\%$ ($N \leq 2$ DLTs), the cohort will be further expanded to a total of 10 patients (3+3+4). The total number of patients for both Arms A and B with full expansions will total of 20. If more than 1/3 or 2/6 patients experience a DLT, there will be no expansion. Safety data obtained from this Phase Ib will be analyzed by the sponsor and collaborating investigators to recommend a Phase II dose.

12.1.2 Phase II:

The study will employ the minimax Simon 2-stage design. In Stage 1, 22 patients will be enrolled. If < 2 patients experience an objective tumor response (defined as CR, or PR, as outlined by the 2007 International Harmonization Project criteria), the study will be discontinued. If 2 or more of the first 22 patients experiences CR, or PR, additional 18 patients will be enrolled in Stage 2. Enrollment into Stage 2 will begin only after least 2 objective response have been observed in Stage 1. (Enrollment into Stage 2 need not be delayed until the response status of all 22 Stage 1 patients is known.) The design parameters are as follows:

- 0.15: unacceptable response rate.

- 0.25: target response rate.
- $\alpha = 0.05$: the probability of declaring the drug effective when the true response probability is less or equal to 0.15.
- $\beta = 0.20$: the probability of declaring the drug as not effective when its true response probability is as large or larger than the target response rate 0.30.

Once enrollment begins for stage 2 of the study, an additional 20 patients will be enrolled per lymphoma subtype, specifically Mantle Cell Lymphoma. Therefore the total number of patients estimated to be enrolled is 60.

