12.3.2 Phase II

12.3.2.1 Primary Objective: Activity Analysis

Efficacy endpoints in this study include defining the proportion of patients with disease response (CR+PR).

CR, PR, and SD are to be determined according to the International Harmonization Project revised Criteria (2007), Patients who discontinue the study before response evaluation will be considered un-evaluable.

In the expansion cohort, analysis for activity in mantle cell lymphoma will be measured for proportion of patients with disease response (CR+PR) determined according to the International Harmonization Project revised Criteria (2007). Patients who discontinue the study before response evaluation will be considered un-evaluable.

For responding patients, the duration of response and time to progression will be reported on a per-patient basis.

Data that may further characterize the activity of ACY-1215 will be summarized and assessed for a potential dose-response relationship.

Overall response rates will be estimated upon completion of the study along with exact 95% confidence intervals.

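### Section 10.4.2 gives response definitions that do not match the named IHP 2007/Table 5 standard for CR+PR, and no rule says how the two fit together

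*Combined protocol and SAP*

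**What the plan says.** The response standard is named consistently. The Synopsis (Study Endpoints), Section 5.1.3 and Section 12.3.2.1 all name the IHP 2007 criteria. Section 12.1.2 defines the response that opens Stage 2 as CR or PR "as outlined by the 2007 International Harmonization Project criteria". The opening of Section 10 says response is evaluated "as defined by the guidelines of the International Harmonization Project Group 2007 Revised Response Criteria". Section 10.4.1 adds: "Table 5 outlines the response criteria used to evaluate disease response to therapy". For nodal PR, Table 5 asks for "50% decrease in SPD of up to 6 largest dominant masses; no increase in size of other nodes".

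Section 10.4.2 then lists three categories under a general heading about response definitions:

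- CR: all non-target lesions gone on PET/CT.
- "Incomplete Response/Stable Disease (SD): Persistence of one or more non-target lesion(s) and/or maintenance of tumor marker level above the normal limits".
- PD: a new lesion, or clear progression of existing non-target lesions. Progression confined to non-target lesions is to be confirmed later.

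Three other provisions bear on this. Section 10.3.1 caps target lesions at six, makes every further lesion non-target, and requires only that each non-target lesion be noted as present or absent. Section 10.1 lets the investigator use CT or PET/CT. Section 10.4.3 makes best response depend on confirmation as well as measurement, and Section 10.4.4 computes the response rate from best response.

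**The concern.** The endpoint is CR+PR, yet the section that appears to define response has no PR and treats any persisting non-target lesion as incomplete response or SD. A reader who takes 10.4.2 at its word can score the same scans differently from one who uses Table 5. The same count decides whether Stage 2 opens and whether the drug is judged active, and it is the activity measure in the 20-patient mantle cell cohort. A scoring rule that is settled only after the scans have been read also leaves room for choice in an open-label, single-arm study.

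**Working it through.** The plan states no figure on this point, so the check sets the provisions side by side. IHP 2007 is taken only as Table 5 reproduces it.

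| Item | Table 5 (10.4.1) | Section 10.4.2 |
|---|---|---|
| Lesions covered | Nodal masses, spleen/liver, marrow | Non-target lesions only |
| CR | By PET, or by regression to normal size on CT in variably avid or PET-negative disease | By PET/CT only |
| PR | Defined; other nodes must not enlarge | No such category |
| Persisting, stable extra node | Compatible with PR | Incomplete Response/SD |
| Tumor marker | Not used | Can by itself give SD; no marker is defined for response |

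**Classification example (illustrative sizes).** Six target nodes measure 30 x 20 mm at baseline and 20 x 12 mm at follow-up.

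- Baseline SPD = 6 x 30 x 20 = 3600 mm².
- Follow-up SPD = 6 x 20 x 12 = 1440 mm².
- Fall = (3600 − 1440)/3600 = 2160/3600 = 60%.

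A seventh node of 15 x 12 mm is unchanged, and there is no new site. The six-lesion cap in 10.3.1 makes that node non-target. By Table 5 the fall exceeds 50% and no other node has grown, so the patient is PR and counts. By 10.4.2 a non-target lesion persists, so the literal label is Incomplete Response/SD and the patient does not count.

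**Recording.** To apply the Table 5 rule to the seventh node, someone must note whether it grew. The entry required by 10.3.1 (present or absent) cannot show that. It is enough for the persistence test in 10.4.2 but not for PR.

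**Confirmation.** Provisions for confirming a finding exist for CR (repeat imaging in 10.1, marrow in 10.2, 10.3 and the study calendar) and for non-target progression (10.4.2). There is none for PR, although 10.4.3 refers to confirmation without limiting it.

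**What one rescored patient does.** Section 12.1.2 opens Stage 2 at 2 responses in 22. Taking one away gives 1 in 22 (2/22 = 9.1%; 1/22 = 4.5%), and on that count rule the study stops. At the end, if the 8 responses are read as 8 of all 40 patients, one fewer moves 8/40 = 20.0% (exact 95% CI 9.1 to 35.6%) to 7/40 = 17.5% (7.3 to 32.8%). The 8-of-40 reading is an interpretation: the Synopsis and Section 5.1.2 print the 8 next to the 18 Stage 2 patients. These figures show what one patient does at a threshold, not how often it would happen.

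**The case against.** The best reply is that the standard is already fixed. The Synopsis and Sections 5.1.3, 10, 10.4.1, 12.1.2 and 12.3.2.1 all point to IHP 2007 or Table 5, including for the Stage 2 decision and the mantle cell cohort. Every category in 10.4.2 speaks of non-target lesions, it follows a section on measurable disease, and without a PR category it could not produce the endpoint in 10.4.4. As a component, an incomplete non-target response is compatible with an overall PR. This largely stands, and it limits the severity. It does not remove the point, because no passage labels 10.4.2 as a component, ranks it below Table 5 or gives a combining rule.

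On recording, it can be said that measuring non-target lesions is optional rather than barred, that the scans remain available, and that the PD line already calls for judging non-target progression. That is fair, but a node can enlarge without unequivocal progression, and the required entry would not show it.

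Some stronger inferences are tempting and are not supported:

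- *A patient could be scored CR with unchanged target lesions.* 10.4.2 read in isolation allows it, but Table 5 requires all evidence of disease to be gone, so this is not a plausible scoring.
- *Whether an unconfirmed PR counts cannot be determined.* The ordinary reading of 10.4.3 is that confirmation is needed where the protocol provides for it, and it provides none for PR. The wording is loose, not contradictory.
- *Hodgkin's lymphoma has no response standard because Table 5 is titled for NHL.* Sections 12.1.2 and 12.3.2.1 apply IHP 2007 to all patients.

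**Conclusion.** The mismatch is real and touches the primary endpoint: 10.4.2, applied literally, would score some Table 5 partial responders as Incomplete Response/SD. In addition, the required lesion record does not capture one of the conditions for PR. A reader might infer that the trial has two rival endpoint definitions of equal standing, or that power is lost. The documents support neither. IHP 2007/Table 5 is the named standard throughout, and nothing says how many patients will have persisting non-target lesions, so no share of rescored responders and no loss of power can be given. Severity is low to moderate. The conclusion assumes that Table 5 reproduces the IHP 2007 criteria faithfully on these points.

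**What to change.** - In 10.4, state that Table 5/IHP 2007 alone determines overall CR, PR, SD and PD for the response rate.
- Relabel 10.4.2 as non-target lesion status that feeds that assessment. Keep its progression rule and the later confirmation of it, and delete the tumor-marker wording.
- In 10.3.1 and on the lesion form, record each non-target lesion as absent, present and not enlarged, or enlarged.
- In 10.4.3, say that confirmation applies only where the protocol states it (CR and non-target progression), so that an unconfirmed PR counts.

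Make the changes before further responses are scored and before the Stage 2 decision, and document the rule used for any response already scored. The cost is wording plus one lesion-form category; no extra scans are needed.
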